## **Data Collection Methods**

Measurements took place on three occasions, (1) baseline, on the first session; (2) 15 minutes, after the first intervention (acute phase); and (3) after four weeks (chronic phase). In addition, (1) age, (2) height, (3) weight and (4) and injury occurrence rate was recorded for each footballer. On the other hand, flexibility, agility and maximal

voluntary muscle strength measures were taken in the same manner and time for all participants across groups.

[figure not shown]
All measurements were taken by one assessor who didn't know at the time of testing to what group the data belonged to. In addition, this assessor was not involved in the implementation of any of the techniques in this study.

**Flexibility.** Extensibility of the hamstrings muscle represented knee flexibility.

Hamstrings muscle injury is common in sports requiring running. It is usually, the result of a muscle imbalance where the quadriceps muscle is strong and hamstrings are weak and inflexible, what puts a great deal of pressure on the hamstrings leading to injury and strain. Straight leg raise (SLR) is a widely used outcome measure used to assess the extensibility of the hamstrings muscle, where its high reliability makes it an easy and reliable method ICCs of 0.96, and high SEM values (2.2°) and MDD (6°). SLR was first applied to all participants across the groups. All football players laid supine and taught to relax during testing. The tested limb was raised by a volunteer therapist with the knee in full extension and the foot in a relaxed position. The other lower limb was stabilized in a neutral hip rotation and full knee extension by another volunteer. The test was stopped once the therapist felt a strong resistance, or when the pelvic rotation was noted. Then, the assessor placed the goniometer over the greater trochanter, with one arm aligning the lateral femoral condyle, and the other arm aligning parallel to the ground, in a direction to the mid-axillary line and recorded the hip angle. The scores were recorded as degrees of range of movement.

**Agility.** Agility was chosen to represent the footballer's performance. This athletic event involves elements of speed, change of direction, and varying types of movement. After the measurement of the extensibility, agility was measured by the T-Drill test. The T-Drill has been proven to be a highly reliable testing measurement, ICC (0.95 with 95 % confidence interval). Footballers were instructed on how to perform the T-Drill and on the test procedures. Then, they were instructed to jog for 2 min to warm-up. The participants performed the T-drill twice and the trial with the best time was taken for analysis by the mean of an alert assessor with a stopwatch. Results were measured in seconds and scores were interpreted as (1) excellent, < 9.5; (2) good, 9.5-10.5; (3) average, 10.5-11.5; and (4) poor, > 11.5. A diagram of the T-Drill with its dimensions are shown in (Figure 2).

**FIGURE 2.** Diagram of T-Drill procedure.

**Strength.** Finally, maximal voluntary muscle strength was measured by one repetition maximum (1RM) tests. The ICC for 1-RM test-retest measures was (0.983, 95% confidence interval= 0.964–0.997. After a rest time of 5 min, participants were

guided to the knee flexors strengthening machine (hamstrings curl machine).

Resistance was placed just proximal to the posterior part of the calcaneus bone.

Footballers performed first specific warm-up, consisting of a set of ten repetitions of knee flexion, with a light load. Afterwards, for safety reasons, an estimation of hamstring 1RM was calculated using Brzycki formula [Weight lifted  $\div$  (1.0278 - (0.0278  $\times$  Number of repetitions)]. This formula exhibited a relatively low level of bias (1.6 to 0 kg) and had an ICC above 0.97 and the lower end of the 95% confidence interval was above 0.94.

Maximal voluntary strength was recorded in kilograms.

## **Data Analysis**

Data were analyzed using the Statistical Package for the Social Sciences (SPSS) version 21.0 for Windows. Descriptive statistics (mean, standard deviation) were calculated to characterize participants' age, weight, and height. Means of the main key variables of the study were also calculated. The Shapiro-Wilk test was used to check the normality of the data distribution. A probability (p) value of  $>0.05$  means that there was no significant difference between groups.

To check for any difference in the incidence of muscle injury between each of the intervention groups, Fisher exact test was used because expected cell count was less than 5.

Dependent t-tests were used to determine any significant differences between the acute and chronic phases of extensibility, agility and muscle strength, and to check the difference between the baseline and chronic phases of these dependent variables.

Analysis of variance (ANOVA) test was used to check for any significant difference between the interventions groups and each of the extensibility, agility, and strength. This test was repeated for three different phases (baseline, acute and chronic). Moreover, after a statistically significant difference was shown between the variables, Tukey's Post Hoc test was used to show where the differences occurred between intervention groups.

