## Procedure

In order to recruit the participants, gyms and football clubs across South-Lebanon and Damascus-Syria were visited and information sheets were distributed. These sheets, (1) explained the study purpose, (2) stressed on the voluntary participation and the free will to withdraw from the study, (3) described the experiment process and its duration; (5) stated possible risks and benefits, (6) stressed over confidentiality and (7) provided investigators contact methods.

To start with the experiment, each enrolled participant signed a consent form. Then, an independent examiner who was not involved in the enrollment process had systematically allocated participants into one of the three intervention groups, by withdrawing names randomly out of a bowl. The first draw was assigned to the static stretching group; the second draw assigned to the dynamic stretching group; the third draw assigned to the DTFM group, and so on. In addition, the investigator who entered eligible participants in the study was not aware of which group they were allocated.

The experiment took place in July 2017, over a four weeks period, and participants in each group followed their intervention protocol three times a week, for a total of 12 sessions.

**Static stretching group.** Static stretching was chosen for its effectiveness in increasing both acute and chronic extensibility. All participants laid on the floor in a supine position with both feet pointing upwards. The tested limb was in full knee extension and the foot in a relaxed position and was moved up passively to a point of slight pain or discomfort at the posterior aspect of the thigh. This technique puts the

hamstrings muscle at its greatest possible length. According to the American College of Sports Medicine (ACSM), this position should be held for 30 seconds and was performed three times for a total of one minute and 30 seconds, 15 minutes after a match or training. The contralateral leg was stabilized by means of another collaborator in order to prevent compensation by rotation or elevation of the pelvis.

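### Between-technique contrasts are planned only after a significant ANOVA, so a non-significant acute or chronic result would come with no planned interval for the differences

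*Combined protocol and SAP*

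**What the plan says.** Four statements in Data Analysis settle how a comparison between techniques would be reported.

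- **Threshold.** A p-value above 0.05 "means that there was no significant difference between groups". This is the only guidance on reading a non-significant result.
- **Test.** The ANOVA "test was used to check for any significant difference between the interventions groups and each of the extensibility, agility, and strength", and "This test was repeated for three different phases (baseline, acute and chronic").
- **Pairwise contrasts.** These are conditional: "after a statistically significant difference was shown between the variables, Tukey's Post Hoc test was used to show where the differences occurred between intervention groups".
- **Summaries.** Mean and standard deviation are planned for age, weight and height. For the outcomes the text says only: "Means of the main key variables of the study were also calculated".

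No confidence interval for a between-group difference, and no margin for calling techniques similar, appears in the text available for review. The intervals under Agility and Strength belong to published reliability coefficients. The dependent t-tests compare phases, not techniques, so they do not fill the gap.

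For flexibility, Data Collection Methods cites "ICCs of 0.96, and high SEM values (2.2°) and MDD (6"°), as evidence that the straight leg raise is reliable.

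**The concern.** All three arms are active techniques, so a non-significant comparison between them is a plausible result and one that readers would want to use. It can arise in two ways: the techniques may perform much alike, or the comparison may be too imprecise to separate them. Only an interval for each difference tells these apart. The plan makes the pairwise analysis conditional on significance, so the intervals are absent in the case where they are needed most.

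The point covers extensibility, agility and strength at the acute and chronic phases. It does not concern the baseline ANOVA or the Fisher exact test for injuries.

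**Working it through.** The text available for review gives no sample size, power or target difference, so there is no planned figure of that kind to reproduce. The reporting gap itself follows from the text. The arithmetic below only illustrates how wide the missing intervals could be for flexibility.

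**Inputs from Data Collection Methods (Flexibility):** SEM 2.2°, ICC 0.96, MDD 6°.

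**Check of the cited MDD:** 1.96 × √2 × SEM = 1.96 × 1.414 × 2.2 = 6.1°, in agreement with the stated 6°. This formula gives the measurement-error limit for repeat tests on one person.

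**Implied between-player SD:** SEM / √(1 − ICC) = 2.2 / √0.04 = 2.2 / 0.2 = 11°. This is derived from a cited reliability source. It is not stated for this trial's players.

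**Tukey simultaneous 95% half-width** for a pairwise difference, three equal arms of n: q(0.95; 3, 3n − 3) × SD / √n. Equal arms follow from the rotating draw described in Procedure; n is assumed.

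| n per arm | q | SD 6° | SD 8° | SD 11° | SD 14° |
|---|---|---|---|---|---|
| 10 | 3.506 | ±6.65° | ±8.87° | ±12.20° | ±15.52° |
| 20 | 3.403 | ±4.57° | ±6.09° | ±8.37° | ±10.65° |
| 30 | 3.372 | ±3.69° | ±4.93° | ±6.77° | ±8.62° |
| 40 | 3.357 | ±3.18° | ±4.25° | ±5.84° | ±7.43° |

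Worked example: at n = 20 and SD 11°, 3.403 × 11 / √20 = 8.37°. Two techniques with identical observed means would then still be compatible with a true difference of about 8° in either direction. The half-width is proportional to the SD, so at SD 6° the same arm size gives ±4.57°.

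**How far a miss rate depends on the unknowns.** Suppose one technique differs from the other two by 6° (means 0, 0, 6; overall mean 2; sum of squared deviations 4 + 4 + 16 = 24). The ANOVA noncentrality is n × 24 / SD². At 20 per arm (2 and 57 degrees of freedom, alpha 0.05):

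- SD 11°: 20 × 24 / 121 = 3.97, and the ANOVA misses the difference 61% of the time.
- SD 6°: 20 × 24 / 36 = 13.33, and it misses it 10% of the time.

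**The case against.** The best defence is that the plan does nothing unusual. Describing p > 0.05 as no significant difference is ordinary wording, and the sentence sits directly after the Shapiro-Wilk test, so it reads as a general threshold rather than a rule for the acute and chronic ANOVAs. Running Tukey after a significant omnibus test is a common convention. Because group means are planned, each pairwise difference can be obtained by subtraction.

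Much of this stands, and it rules out several stronger readings.

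- A reader might infer that the plan would declare the techniques alike. It says nothing of the kind; that step would be the reader's.
- A reader might infer that a null result leaves no estimate at all. The means give point differences; what is missing is the interval.
- A reader might infer that a 6° flexibility difference would often be missed. That rests on an arm size and SD that the available text does not supply, and the miss rate at 20 per arm runs from 10% to 61% between SDs of 6° and 11°. Part of the document was not available, so a sample-size statement elsewhere cannot be ruled out.
- A reader might take the 6° MDD as a ready-made similarity margin. It is an individual measurement-error limit, and the documents never argue that a mean difference below it is unimportant.

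The defence does not supply the interval. A general threshold still applies to the acute and chronic comparisons, and means without a planned SD or interval do not convey precision.

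**Conclusion.** The point holds as a reporting gap. Under the plan as written, a non-significant acute or chronic comparison would be reported as such, with no planned measure of which differences between techniques the data still allow. This follows from the text alone and does not depend on power.

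Its practical size cannot be fixed from the available text. At the implied SD of 11°, the unreported Tukey half-width for flexibility would run from about ±12.2° at 10 per arm to ±5.8° at 40. These figures assume three equal arms, a common SD, and that the cited reliability data describe this trial's players. The documents give no comparable basis for an illustration on agility or strength, but the same gap applies to them.

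**What to change.** In Data Analysis, remove the condition on the pairwise contrasts for the acute and chronic phases. For extensibility, agility and strength at each of these phases, report the static–dynamic, static–massage and dynamic–massage mean differences with Tukey simultaneous 95% confidence intervals, whether or not the ANOVA is significant.

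Add a sentence that p > 0.05 alone does not show that the techniques are similar. Make no similarity claim for any outcome unless the sponsor has justified a between-group margin in advance. The 6° MDD may be cited as context for the flexibility intervals, not as that margin.

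The cost is one extra output table per outcome, with no new data or players. The downside is that some null results will read as inconclusive.

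### No paired test compares baseline with the acute measurement, so the acute change has no test or interval

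*Combined protocol and SAP*

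**What the plan says.** Data Collection Methods sets the schedule: "Measurements took place on three occasions, (1) baseline, on the first session", then "2) 15 minutes, after the first intervention (acute phase); and (3) after four weeks (chronic phase". Extensibility, agility and strength are measured at each occasion. The Agility and Strength paragraphs describe a short jog, two T-Drill runs, a rest, a light warm-up set and an estimated 1RM on the curl machine. No shortened battery is described for the acute occasion.

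Data Analysis names two paired contrasts. The first is "Dependent t-tests were used to determine any significant differences between the acute and chronic phases of extensibility, agility and muscle strength". The second is "to check the difference between the baseline and chronic phases of these dependent variables". It does not say whether these tests are run within each arm or on all players together.

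The acute data have one other use, a between-group ANOVA: "This test was repeated for three different phases (baseline, acute and chronic". Tukey comparisons follow if it is significant. No change score, baseline-adjusted model or repeated-measures model is described.

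**The concern.** An acute response is the difference between a player's acute score and that player's baseline score. The plan collects both scores and gives the second occasion its own label. Procedure also justifies static stretching partly by its acute effect. Yet no planned analysis attaches a p-value or interval to that difference.

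The paired contrast that does use the acute score answers another question. Chronic minus acute is the chronic change minus the acute change: how much was gained or lost after the first session. A report built on this plan could discuss acute effects using only that contrast and a between-group comparison of levels. Neither shows whether players moved from baseline.

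**Working it through.** **Inputs.** The three occasions come from Data Collection Methods. The two paired contrasts, the ANOVA and the 0.05 threshold come from Data Analysis. The plan gives no sample size, SD or effect size for these contrasts, so there is no planned figure to reproduce.

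**1. Which pairs are tested.** Write B, A and C for baseline, acute and chronic.

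- A versus C: tested.
- B versus C: tested.
- B versus A: not tested.

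**2. Can the missing result be rebuilt from the other two?** The mean can: A − B = (C − B) − (C − A). Take an assumed SLR of 70° at baseline and 76° at both later occasions, a gain equal to the stated minimal detectable difference of 6°. Then C − B = 6°, C − A = 0° and A − B = 6 − 0 = 6°.

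The test cannot. Set the SD of each reported difference to 1 and let r be their correlation. The SD of A − B is √(1 + 1 − 2r):

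- r = 0: √2.0 = 1.41
- r = 0.5: √1.0 = 1.00
- r = 0.9: √0.2 = 0.45

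The SD varies about threefold with r, and the plan does not provide for reporting r.

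**3. Does the acute-phase ANOVA fill the gap?** It compares three group means at one occasion. If all three techniques raised SLR by the same amount, the expected group differences would be zero, as they would be if none did anything. Baseline values are not used. Procedure describes three active arms and no untreated one.

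**4. What a same-session repeat battery would do.** Baseline falls on the first session and the acute tests 15 minutes after the first intervention, so both appear to fall in one visit. This timing is inferred. Assume true acute and chronic effects of 3° each, and a shift s in the acute score from the earlier battery (fatigue, warmth or practice):

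- s = −2°: A − B = 3 − 2 = 1; C − A = 3 − 1 = +2; C − B = 3
- s = 0°: A − B = 3; C − A = 0; C − B = 3
- s = +2°: A − B = 3 + 2 = 5; C − A = 3 − 5 = −2; C − B = 3

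The shift enters both contrasts that use the acute score, including the one to be added.

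**5. How often such a shift alone would give a significant acute-versus-chronic test.** Assume no technique effect, a two-sided 0.05 paired t-test within one arm, and a shift of d SDs of the paired difference. The rate comes from the noncentral t with n − 1 degrees of freedom and noncentrality d√n:

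- d = 0.2: 9% (n = 10), 11% (n = 15), 14% (n = 20)
- d = 0.3: 14%, 19%, 25%
- d = 0.5: 29%, 44%, 56%

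Both d and n are assumptions.

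**6. Cost in number of tests.** With three outcomes, adding the third pair takes the paired tests from 2 × 3 = 6 to 3 × 3 = 9 if pooled, or from 18 to 27 if run in each of three arms. Without adjustment, and treating tests as independent (they are not), the chance of at least one false positive is 1 − 0.95^k:

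- k = 6: 0.265
- k = 9: 0.370
- k = 18: 0.603
- k = 27: 0.750

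**The case against.** The best defence is that the acute data are analysed. Under random allocation, an ANOVA at the acute phase is a legitimate between-arm comparison bearing on acute response. That stands, so a reader should not infer that the acute measurement goes unexamined. But the ANOVA is less efficient than a baseline-adjusted comparison and says nothing about whether any arm changed.

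A reader might also infer that the plan cannot tell equal acute and chronic benefit from no benefit, because acute versus chronic is zero in both cases. The documents do not support this: baseline versus chronic is also planned, and it gives 6° in the example above against 0° with no benefit. What is missing is narrower, namely the test and interval for the acute change.

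Nor does acute versus chronic have to be deleted. Whether players gain or lose between the first session and the end of the programme is a fair question.

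The fatigue argument is partly conjecture. The 1RM is estimated by formula, the warm-up and rest partly standardise test conditions, and a figure in Data Collection Methods is not available here. A repeat-battery effect is plausible, but its direction and size are not known.

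**Conclusion.** The omission is plain from the text. Three occasions are measured and two of three pairs are tested; the pair left out defines the acute change. The acute-phase ANOVA does not replace it. This should be corrected, although the four-week change does have its own paired test.

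Two stronger readings go too far. The first is that a repeat-battery effect would be common to all arms and cancel in between-arm comparisons. Procedure places static stretching after a match or training, dynamic stretching in the warm-up and the friction massage before exercise. If the first session followed that pattern, test-day state could differ by arm and the effect need not cancel. The second is that acute versus chronic has a known inflated false-positive rate. The rates run from about 9–14% at an assumed shift of 0.2 SD to 29–56% at 0.5 SD, for an assumed 10–20 players per arm. They show sensitivity and do not establish that a shift occurred.

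The omission itself needs no numerical assumption. The caution about interpretation rests on the inferred same-session timing. The pages reviewed contain no objectives section, so interest in an acute effect is inferred from the schedule and the rationale in Procedure.

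**What to change.** In Data Analysis:

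- Add the baseline-to-acute change for each outcome, with a 95% confidence interval, and state whether paired tests are run per arm or pooled.
- Compare arms at the acute and chronic phases with ANCOVA adjusted for baseline, or with one group-by-time repeated-measures model, in place of the separate ANOVAs on levels.
- Name a multiplicity procedure that covers the added contrast, for example Holm across the paired tests.
- Keep acute versus chronic, if wanted, as a secondary description. State that neither it nor the within-arm acute change isolates a technique effect, because the acute tests appear to follow a full baseline battery.
- Attach to between-arm acute comparisons the caveat that the techniques sit at different times relative to exercise. State when each battery took place in each arm.

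The data are already collected, so the cost is analysis time and a larger set of tests (9 for 6, or 27 for 18). Multiplicity control will cost some power for each contrast. Neither ANCOVA nor the group-by-time model can supply the missing untreated comparison, so the results remain comparisons between techniques.

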**Dynamic stretching group.** The dynamic stretching technique was included for its positive effects on agility and muscle strength. Participants in this group, swung their tested leg actively into hip flexion while keeping their knee fully extended and their ankle fully plantar flexed, until a stretch was felt in the posterior thigh. This was repeated over 30 seconds and included in the participant's warm-up phase.

**Deep transverse friction massage group.** Participants were taught by one of the examiners how to sit and perform pre-exercise self-massages on their tested leg MTJ. The procedure consisted of applying friction massage by fingertips transversely to the hamstrings tendon, in a sitting position. The tendon was located over four finger widths proximal to the medial and lateral epicondyles of the femur. One examiner carefully monitored how the technique was performed to assure the precision of the application. This massage technique was applied over a duration of 30 seconds.

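### Change over four weeks is tested only by paired t-tests, which cannot separate a technique effect from training or test practice, and the planned between-arm ANOVA makes no use of baseline

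*Combined protocol and SAP*

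**What the plan says.** **Tests of change.** Under Data Analysis, "Dependent t-tests were used to determine any significant differences between the acute and chronic phases" of extensibility, agility and strength, and also "to check the difference between the baseline and chronic phases of these dependent variables". No other test of change over time appears. The section does not say whether these tests are run within each arm or on all players together, or what may be concluded from a significant result.

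**Between-arm tests.** The same section plans an ANOVA across the intervention groups for each of the three outcomes, repeated separately at baseline, acute and chronic phases, with Tukey's test after a significant result. It mentions no change score, baseline covariate or group-by-time term.

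**Arms.** Under Procedure, an examiner "systematically allocated participants into one of the three intervention groups" by drawing names: static stretching, dynamic stretching or deep transverse friction massage. Every arm is active.

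**Setting.** The trial ran "over a four weeks period, and participants in each group followed their intervention protocol three times a week, for a total of 12 sessions". Players assigned to static stretching did it "15 minutes after a match or training", dynamic stretching was "included in the participant's warm-up phase", and the massage was done before exercise.

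**Testing.** Under Data Collection Methods, the same measurements are taken on three occasions. For agility, "The participants performed the T-drill twice and the trial with the best time was taken for analysis", after instruction and a short jog. No earlier familiarisation session is described.

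**The concern.** A paired t-test asks whether the mean changed. It cannot say why. The techniques are attached to matches, training and warm-ups, so players evidently went on with ordinary football. By the four-week visit each player had also been through the test battery twice. Baseline-to-chronic change is therefore the sum of any technique effect, any training effect and any practice effect. With no untreated arm, nothing in the paired test separates them.

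The ambiguity over pooling does not rescue the test. Pooled over arms, it says nothing about any one technique. Run per arm, it tempts the reader to compare p-values across arms, although one arm below 0.05 and another above it is not evidence of a difference between them.

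The comparison that removes shared drift is the one between randomised arms. The plan has one at four weeks, but on raw levels, so differences between players that were already there at baseline remain in the error term.

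**Working it through.** The available text gives no sample size, power or effect size, so there is no design figure to reproduce. Group size and drift below are assumptions. Tests are taken as two-sided at 0.05; the plan gives the 0.05 but not the sidedness.

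**1. Paired tests when no technique does anything.** Let every arm drift by d, in SDs of the paired differences. The paired t statistic is then noncentral t with n−1 degrees of freedom and noncentrality d√n. With per-arm rejection probability p and independent arms, P(at least one of three) = 1 − (1−p)³.

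| Drift d | n per arm | d√n | Per arm | At least one arm |
|---|---|---|---|---|
| 0.3 | 10 | 0.95 | 14% | 36% |
| 0.3 | 15 | 1.16 | 19% | 47% |
| 0.3 | 20 | 1.34 | 25% | 57% |
| 0.5 | 10 | 1.58 | 29% | 65% |
| 0.5 | 15 | 1.94 | 44% | 82% |
| 0.5 | 20 | 2.24 | 56% | 92% |

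Smaller drifts do less: at 0.2 SD the ranges are 9–14% and 24–35%; at 0.1 SD, 6–7% and 17–20%. If the tests are run per arm, a mixed result (some arms significant, others not) has probability 1 − p³ − (1−p)³, which is 35–56% at 0.3 SD and 62–74% at 0.5 SD.

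**2. What such a drift means in degrees.** For the straight leg raise, Data Collection Methods gives SEM 2.2° and MDD 6°. Check: 1.96 × √2 × 2.2 = 6.1°, which agrees. With measurement error alone, the SD of a paired difference is √2 × 2.2 = 3.11°. If individual responses also vary, it is larger; take 6° as an assumption. Then 0.3 and 0.5 SD are 0.9° and 1.6° (SD 3.11) or 1.8° and 3.0° (SD 6), all well below the stated MDD.

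**3. Between-arm tests under the same shared drift.** In 5,000 simulated trials per setting (straight leg raise, between-player SD assumed 10°, drift 2° or 3°, 15 or 20 per arm), ANOVA on chronic levels rejected in 4.6–5.4% and ANOVA on change in 4.7–4.9%. Both hold the nominal 5%.

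**4. What ignoring baseline costs.** The stated ICC of 0.96 and SEM of 2.2° imply a total SD of 2.2/√(1 − 0.96) = 11°, assuming both figures refer to players like these. Suppose one arm gains 6° more than the other two, with 15 per arm. The arm means 6, 0, 0 have squared deviations 16 + 4 + 4 = 24, so the F noncentrality is 15 × 24/SD², with critical F(2, 42) = 3.22.

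- Chronic levels, SD 11: 360/121 = 2.98, power 30%. If response variation raises the SD of differences to 6 and all of the extra variance (36 − 9.68 = 26.32) falls on the chronic value, the level SD is √(121 + 26.32) = 12.1 and power is 25%.
- Change, SD 6: 360/36 = 10.0, power 79%.
- Change, SD 3.11: 360/9.68 = 37.2, power above 99%. This is optimistic, since it allows no variation in response.

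**The case against.** The strongest reply is that the plan already contains the right kind of comparison. The chronic-phase ANOVA with Tukey tests compares randomised arms, is unaffected by drift shared across arms, and is the stated way of locating differences between techniques. This stands. A reader might infer from the paired tests that the plan has no valid technique comparison at four weeks; the Data Analysis section does not support that. What remains against the ANOVA is loss of precision and exposure to chance baseline imbalance.

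A reader might also infer that the plan will credit a significant paired change to the technique, or rank techniques by which arm reached significance. No passage says so, and Tukey's test is the named tool for ranking. The supportable statement is that a paired change could not be separated from a technique effect, and that the plan sets no limit on its interpretation. Aims and intended conclusions are not in the available text and cannot be checked.

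Third, drift is not quantified anywhere in the documents. Practice is less plausible for the straight leg raise, a passive test, than for the T-Drill or the strength test, and the two T-Drill runs per visit give some practice within the visit. The quoted reliability coefficients are high (0.95 to 0.983), but a high ICC does not exclude a systematic shift. So the rates above are illustrations, and at 0.1 SD the per-arm inflation is slight.

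**Conclusion.** The point holds as a limit on what the paired tests can show, together with a weakness in the between-arm test. The paired tests cannot answer whether any technique works, however they are run. The false-positive ranges depend wholly on the assumed drift and group size, and the mixed-result figures also on the tests being run per arm.

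The between-arm ANOVA is valid under shared drift but wasteful: in the illustration, about 25–30% power on levels against 79% to over 99% on change, assuming 15 per arm and a 6° advantage in one arm. Without an untreated arm, no analysis of these data can show that a technique beats ordinary training. Severity: should-fix.

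**What to change.** 1. State that four-week conclusions about techniques rest on between-arm differences adjusted for baseline: ANCOVA of the chronic value on group and baseline, or ANOVA on change from baseline. Choose one in advance, and give pairwise differences with 95% confidence intervals under Tukey-type multiplicity control.
2. Report the paired changes descriptively, per arm, as mean change with confidence interval, and state that they do not by themselves show a technique effect.
3. Limit conclusions to the relative effects of the three techniques, and say that no arm was untreated.

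The cost is a little more analysis on data already collected, plus giving up statements that a given technique improves a given outcome.
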